# PPD

where “*total number of capsules taken during the treatment period*” is the sum of number of capsules taken at each cycle (CRF IMP ACCOUNTABILITY form), while the “*total number of capsules dispensed during the treatment period*” is given by the number of dispensed kits (CRF IMP DISPENSATION form) considering that each kit contains 56 capsules.

For a complete treatment period over 13 cycles the dispensed number of capsules and the number of capsules the patient is expected to take is the same and is equal to 728.

For a cycle that is interrupted due to treatment discontinuation the expected #capsules may differ from the # dispensed as follows:

- If interrupted before the expected last intake, the expected # capsules will be derived as:

$$\begin{aligned} \text{Expected # capsules} &= 56 * \# \text{ completed } k \text{ cycles } (k = 1 \dots i - 1) \\ &+ 4 * (\text{Date treatment discont in Cycle } (i) - \text{Data start Cycle } (i) + 1) \end{aligned}$$

In the expected #capsules calculation, it is assumed that the discontinuation occurs after last daily intake.

- If interrupted after the expected last intake, the expected number of capsules will be:

$$\text{Expected # capsules} = 56 * \# \text{ completed } k \text{ cycles } (k = 1 \dots i - 1) + 56$$

IMP intake compliance over the entire treatment period will be summarized by treatment by means of summary statistics.

In addition, compliance to IMP over the entire treatment period will also be presented for the following categories: <80%, 80%-100% (excluded), 100%, >100%.

## 6.1.1.2 By cycle

Compliance by cycle with respect to IMP intake will be assessed following the formula below:

$$\begin{aligned} \text{IMP intake compliance at cycle } (i) (\%) \\ &= \frac{\text{total number of capsules taken during the cycle}}{\text{total number of capsules dispensed during the cycle}} \times 100 \end{aligned}$$

If cycle (i) is completed, the dispensed number of capsules and the number of capsules the patient is expected to take is the same and is equal to 56.

If cycle (i) is interrupted due to treatment discontinuation:

- If interrupted before the expected last intake, the expected number of capsules will be derived as:

$$\begin{aligned} \text{Expected # of capsules} \\ &= 4 * (\text{Date treatment discont in Cycle } (i) - \text{Data start Cycle } (i) + 1) \\ &\bullet \text{ If interrupted after the expected last intake, the expected number of capsules will be 56} \end{aligned}$$

# PPD

## 6.1.1.3 Global criteria for IMP intake compliance

A subject will be classified as “Globally Compliant to IMP intake” (=”Y”) if:

- a) IMP intake compliance over the entire treatment period in the range 80% - 100% (80 and 100 included)  
**AND**
- b) no more than 2 consecutive cycles with IMP intake compliance <80% or >120%  
**AND**
- c) no more than 4 cycles with IMP intake compliance <80% or >120%,

otherwise he will be classified as Non-Compliant (=”N”).

*Note: conditions (b) and (c) to be checked only for patients who completed the entire treatment period.*

The following variables will also be derived:

- #cycles with IMP intake compliance <80% or >120%, (only for patients who completed the entire treatment period).
- 3 or more consecutive cycles with IMP intake compliance <80% or >120% [Y/N], (only for patients who completed the entire treatment period).

## 6.1.2 Compliance to duration of period “ON-treatment”

By study protocol for each cycle each patient is supposed to take IMP for 14 days; compliance to duration of “ON-treatment” period is evaluated as the comparison between the expected duration (14 days) and the actual (observed) duration.

### 6.1.2.1 Over the entire treatment period

Compliance to ON-Treatment period will be calculated as follow:

$$\text{Period ON compliance (\%)} = \frac{\text{Total observed duration of period ON}}{\text{Total expected duration of period ON}} \times 100$$

The total expected duration of period ON for a subject who complete regularly the study is 182 days (14 days \* 13 cycles).

*The actual (observed) duration of k-th period ON (k=1... 13) from each cycle is defined as:*

$$k - \text{th cycle duration ON} = \text{Date last intake in Cycle (k)} - \text{Data start Cycle (k)} + 1$$

# PPD

The observed Total Duration period ON over the entire treatment period is given by the sum of the k periods ON from each cycle.

In case of treatment discontinuation, the last cycle can be affected. Considering the first k completed cycles (k=1.... l-1):

- Expected total duration of period ON =  $14 * k$  [1]
- Actual (observed) Total Duration ON is given by the sum of the k observed periods ON [2].

The last i-th cycle, interrupted due to treatment discontinuation is included as follows:

- If interrupted before the expected last intake, the duration of the period ON to be added to [1] and [2] is derived as:

i-th Cycle Duration ON = Date treatment discontinuation – Data start Cycle (i) +1

With this formula we are assuming that the IMP is taken on the day of discontinuation.

- If the trial will be discontinued after the expected last intake, the expected duration of the i-th period ON is 14 days.

## 6.1.2.2 By Cycle

Period ON compliance at cycle (i) will be calculated as follow:

$$\text{Period ON compliance at cycle (i)(\%)} = \frac{\text{observed duration of period ON at cycle } i}{\text{expected duration of period ON at cycle } i} \times 100$$

The observed duration of period ON for each cycle is defined as:

*Duration period ON, cycle (i) = Date last intake in cycle (i) – Data start cycle (i) + 1*

The expected duration of period ON is 14 days.

For a cycle that is interrupted due to treatment discontinuation the rule to be applied is the same as the one reported above in section 6.1.2.1:

- If interrupted before the expected last intake, the duration of the period ON is derived as:
  - i-th Cycle Duration ON = Date treatment discontinuation – Data start Cycle (i) +1 (if the day of discontinuation the IMP was taken)
  - i-th Cycle Duration ON = Date treatment discontinuation – Data start Cycle (i) (if the day of discontinuation the IMP was not taken)
  - expected duration will be = observed duration
- If interrupted after the expected last intake, the expected duration of period ON is 14 days

*Note:*

*Date start cycle and date last intake in the cycle are considered as they are, regardless of whether the intake of the 1st day occurred only in the evening and the intake of the last day occurred only in*

# PPD

*the morning. This may happen, but conventionally days and not day periods (morning / evening) will be considered. For these cases is possible that intake may last 15 days instead of 14.*

In case the kit was dispensed, it was returned, and the number of capsules taken is 0 (therefore we cannot define the start cycle date and end cycle date), we will follow the following convention:

- Start Cycle x date will be as scheduled date: start cycle x-1 date (previous cycle) +28 days
- End Cycle x date will be equal to start cycle x date
- On period will be set to 0 days

## 6.1.2.3 Global criteria for duration of ON-Treatment period

A subject will be classified as “Globally Compliant to ON-treatment period” (=”Y”) if:

- a) Compliance to Period “ON” duration over the entire treatment period in the range 80% - 120% (80 and 120 included)  
**AND**
- b) no more than 2 consecutive cycles with compliance to “Period ON” duration <80% or >120%  
**AND**
- c) no more than 4 cycles with compliance to “Period ON” duration <80% or >120%,

otherwise he will be classified as Non-Compliant (=”N”).

*Note: conditions (b) and (c) to be checked only for patients who completed the entire treatment period.*

The following variables will also be derived:

- #cycles with compliance to “Period ON” length <80% or >120%, (only for patients who completed the entire treatment period).
- 3 or more consecutive cycles with “Period ON” length compliance <80% or >120% [Y/N], (only for patients who completed the entire treatment period).

## 6.1.3 Compliance to duration of period “OFF”

By study protocol for each cycle each patient is supposed to have a 14-days period OFF treatment after the 14-days ON-treatment period. Compliance to duration of period “OFF” is the comparison between the expected duration (14 days) and the actual (observed) duration.

### 6.1.3.1 Over the entire treatment period

Period OFF compliance will be calculated as follow:

# PPD

$$\text{Period OFF compliance (\%)} = \frac{\text{Total observed duration of period OFF}}{\text{Total expected duration of period OFF}} \times 100$$

The total expected duration of period OFF for a subject who complete regularly the study is 168 days (14 days \* 12 cycles).

The duration of k-th period OFF (k=1,...,12) from each cycle is defined as:

*k – th Cycle Duration OFF*

$$= \text{Date start Cycle (}k + 1\text{)} - \text{Date last intake in Cycle (}k\text{)} - 1$$

The total observed duration OFF is given by the sum of the k periods OFF.

In case of treatment discontinuation during cycle (i):

- If discontinued before last intake of the period ON:
  - Expected Total period OFF=14\*( i-1)
  - Observed Total period OFF=sum from k=1 to i-1 of the i-1 period OFF
- If discontinued after last intake of the period ON:
  - Expected Total period OFF=14\*( i-1) + period OFF for i-th cycle (see [\*])
  - Observed Total period OFF=sum from k=1 to i-1 of the i-1 period OFF + period OFF for i-th cycle (see [\*])

[\*] In case i-th cycle is interrupted due to treatment discontinuation after the expected last intake, the expected and observed duration of period OFF for i-th cycle is derived as:

$$i - \text{th Cycle Duration OFF} = \text{Date trial discontinuation} - \text{Date last intake in Cycle (}i\text{)}$$

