## 7.5.        **EARLY PATIENT WITHDRAWAL**

### 7.5.1.        **Withdrawal criteria**

Patients will be informed that they have the right to withdraw from the study at any time (withdrawal of consent), without prejudice to their medical care, and are not obliged to state their reasons.

If a patient fails to return to the center for a scheduled visit, attempts should be made to contact the patient to ensure that the reason for not returning is not a SAE. Likewise, if a patient declares his/her wish to discontinue from the study e.g. for personal reasons, an attempt should be made to establish that the true reason is not a SAE (bearing in mind the patient is not obliged to state his/her reasons).

Safety laboratory tests should be performed whenever possible at patient withdrawal.

Patients who discontinue the treatment with the IMP will not be withdrawn from the study, but will be asked to complete observations as per the protocol, unless otherwise they withdraw their consent. It is important that any randomized patient remains in the study and is followed for both efficacy and safety outcomes, regardless he/she has completed or discontinued the study treatment.

Investigators will be trained about the importance of patient retention through the duration of the trial.

In case of pregnancy, the patient will be withdrawn from the study, but she will be followed for safety and pregnancy outcomes monitoring, unless she withdraws her consent.

Any withdrawals must be fully documented in the eCRF.

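### SAP 6.1.3.1 runs the last OFF period after treatment discontinuation to trial discontinuation, so follow-up time dilutes the OFF ratio and can class some patients with long gaps as compliant

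*SAP*

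**What the plan says.** **OFF periods.** SAP 6.1.3.1 divides total observed OFF days by total expected OFF days. For a patient who finishes: "The total expected duration of period OFF for a subject who complete regularly the study is 168 days". If treatment is discontinued in cycle i after the expected last intake, both totals gain one further term for that cycle: "the expected and observed duration of period OFF for i-th cycle is derived as" the trial-discontinuation date minus the last intake. If the stop comes earlier in the cycle, no term is added. The only OFF criterion is an overall ratio below 150% (6.1.3.3); there is no by-cycle OFF rule (6.1.3.2).

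**Follow-up after stopping.** Protocol 7.5.1: "Patients who discontinue the treatment with the IMP will not be withdrawn from the study". Protocol 6.4.2 says the same, and the last visit is at Week 78. SAP 5.5 has a separate line for patients who stop IMP and still finish the study.

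**ON periods.** If the stop precedes the expected last intake, 6.1.2.1 adds the same days, counted to the treatment-discontinuation date, to observed and expected. By cycle (6.1.2.2), "expected duration will be = observed duration".

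**By-cycle limits.** For both intake (6.1.1.3) and ON duration (6.1.2.3), "conditions (b) and (c) to be checked only for patients who completed the entire treatment period". Condition (b) allows at most two poor cycles in a row; (c) allows at most four in all.

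**Intake denominator.** The formula in 6.1.1.1 divides by capsules dispensed. The section then derives expected capsules for an interrupted course, without saying that they replace the denominator.

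**Use.** 6.1.4 combines the three global criteria into one yes/no flag, shown by treatment and overall.

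**The concern.** The ratio is meant to describe the treatment period. Once IMP has stopped there is no next cycle to start late, so the days after that carry no information about keeping to the 14-day breaks. Putting them in numerator and denominator alike can only move the ratio towards 100%, and the longer a stopper stays in follow-up, the further it moves.

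The branch is not remote. Discontinuation criteria are checked at Weeks 11, 23 and 35. On the nominal schedule these visits fall in the OFF phases of cycles 3, 6 and 9, where this rule applies.

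At stake is the meaning of the flag. If stoppers and completers are classified by different yardsticks and stopping differs between arms, the by-arm compliance table is harder to read.

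**Working it through.** **1. The plan's own totals.** OFF: 14 × 12 = 168 days. ON: 14 × 13 = 182 days ("The total expected duration of period ON for a subject who complete regularly the study is 182 days"). Capsules: 56 × 13 = 728 ("the number of capsules the patient is expected to take is the same and is equal to 728"). All three reproduce.

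**2. Where the scheduled checks fall.** On the 14/14 schedule the ON phases of cycles 3, 6 and 9 end on days 2×28+14 = 70, 5×28+14 = 154 and 8×28+14 = 238. Weeks 11, 23 and 35 end on days 77, 161 and 245, each inside the following 14-day break.

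**3. The OFF ratio for a stopper.** Let m = i − 1 be the finished OFF periods, L their mean length, and X the days from last intake to trial discontinuation.

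- Ratio = (mL + X)/(14m + X).
- It reaches 150% when L ≥ 21 + 0.5X/m. Without the added term, or for a completer, the threshold is L ≥ 21.
- With m = 5 the threshold is 22.4 days for X = 14, 31 days for X = 100 and 35 days for X = 140.

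**4. Worked case (assumed pattern).** Five breaks of 28 days; IMP stopped after the cycle 6 intake. Last intake is day 5×(14+28)+14 = 224. Week 52 is day 364, so withdrawal then gives X = 140.

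| Treatment of the last OFF period | Ratio | OFF criterion |
|---|---|---|
| Left out (X = 0) | 140/70 = 200% | fails |
| Ended at treatment stop, X = 14 | 154/84 = 183% | fails |
| X = 70 | 210/140 = 150% | fails (limit is below 150%) |
| As written, trial withdrawal at Week 52 | 280/210 = 133% | passes |

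Any X above 70 days reverses the classification.

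**5. No value in some cases.** A patient who stops IMP but completes the study has no trial-discontinuation date, so X is undefined. A stop after the ON phase of cycle 1 gives X/X = 100% whatever happened. A stop before the last intake of cycle 1 gives 0/0.

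**6. ON days of an interrupted cycle (assumed case).** Three full cycles, then capsules for 3 days of cycle 4, with discontinuation dated day 12. As written, overall ON is (42+12)/(42+12) = 100%. Counting observed days to last intake gives (42+3)/(42+12) = 83.3%. Capsule intake already shows the gap: 12/48 = 25% in that cycle and (168+12)/(168+48) = 83.3% overall.

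**7. Consecutive poor cycles (assumed case).** Three consecutive cycles at 50% intake, the rest full.

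- Stopper after 9 cycles: (3×28 + 6×56)/(9×56) = 420/504 = 83.3%. This meets the intake criterion, because (b) is not checked.
- Completer: (3×28 + 10×56)/728 = 644/728 = 88.5%. This fails, on (b) alone.

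**8. Intake denominator.** Kits are issued 3, 3, 3 and 4 at a time (Protocol 6.2). A patient with perfect intake who stops on day 7 of cycle 4 has taken 3×56 + 28 = 196 capsules. Against 6 kits dispensed this is 196/336 = 58.3%, which fails; against expected capsules it is 196/196 = 100%.

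**The case against.** The strongest reply is that *trial* is a slip. The rule is introduced as covering treatment discontinuation, and the parallel ON rule in 6.1.2.1 also says *trial* where the matching bullet in 6.1.2.2 speaks only of interruption. If the treatment-stop date is meant and falls within the 14-day break, X is at most 14, the worked case stays at 183–200%, and the reversal disappears. That is plausible. But the formula is what will be programmed, so the correction is needed on either reading.

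The example is also severe: five breaks in a row at double length. That is fair. It shows the mechanism, not a frequency, and the documents give no data on gap lengths or exit times.

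The ON point is partly covered elsewhere. Missed capsules reduce the intake ratio, and the by-cycle ON value cannot change a stopper's flag while (b) and (c) are waived. In the case worked above, the corrected overall ON value stays within 80–120%. This is a secondary repair.

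The waiver is stated openly and has a rationale for (c), since an absolute limit of four poor cycles suits a 13-cycle course. That rationale does not extend to (b), which can be checked in anyone with three or more started cycles.

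**Conclusion.** The OFF rule for stoppers should be corrected. Taken literally, it counts post-treatment follow-up in a treatment-period measure, can turn 200% into 133% and so reverse the OFF classification, and is undefined for stoppers who complete the study. The size depends on assumed gap lengths and exit dates, and on *trial* being meant literally.

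A reader might infer more than the documents support:

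- **That stoppers with poor adherence generally pass.** They do not. Overall intake must still be 80–100% and overall ON 80–120%; a stopper at 75% in every cycle has 75% overall and fails. What passes is long gaps diluted by follow-up, or poor cycles concentrated enough to leave the overall figure at 80% or more.
- **That the interrupted cycle is always scored 100%.** This holds for the added OFF term and for ON when the stop precedes the expected last intake. It does not hold for capsule intake, nor for ON after the expected last intake, where 14 days are expected.
- **That the rules are uniformly looser for stoppers.** The dispensed-capsule denominator, read literally, works against them.
- **That a Week 78 exit dilutes the ratio further.** A patient who attends the last visit has completed the study and has no trial-discontinuation date, so the rule gives no number.
- **That the trial's reading of intake rests on this flag.** Capsule counts, by-cycle compliance, started cycles, exposure and reasons for stopping are also reported. No analysis set in SAP 4.2 and no efficacy analysis uses the flag, and all analyses are descriptive.

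**What to change.** **Main change, SAP 6.1.3.1.** Leave the unfinished last OFF period out of both totals, or end it at the treatment-discontinuation date. Leaving it out is cleaner. State that OFF compliance is not assessable for a patient with no finished OFF period, and how 6.1.4 then sets the flag.

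**Secondary changes.**

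- *6.1.2.1 and 6.1.2.2:* for a stop before the expected last intake, count observed ON days to the last intake date and expected ON days to the discontinuation date, with a maximum of 14. The last intake date is already derived from the diary in SAP 9.1.
- *6.1.1.3 and 6.1.2.3:* apply (b) to all patients over the cycles they started, or show the flag separately for completers and stoppers. Do not scale (c) by 4/13: with three started cycles that allows 3 × 4/13 = 0.92 of a cycle, so one poor cycle would fail although (b) tolerates two in a row.
- *6.1.1.1 and 6.1.1.2:* state that expected, not dispensed, capsules are the denominator for stoppers.

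**Cost.** A few lines of SAP text and small programming changes, with no new data. Some stoppers may change category in either direction. If the database is already locked, the change can be reported as a documented deviation in the clinical study report.

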## 6.1.3.2 By Cycle

No compliance by cycle defined for the “OFF-Treatment”.

## 6.1.3.3 Global criteria for duration of OFF-Treatment period

A subject will be classified as “Globally Compliant to OFF-treatment period” (=”Y”) if:

- a) Compliance to “OFF-Treatment” duration over the entire treatment period is <150%  
otherwise he will be classified as Non-Compliant (=”N”).

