### 6.2. IMP DISPENSATION

The IMP will be dispensed quarterly only by the Pharmacist (or authorized designee at site).

The IMP will be dispensed via IRS as Patient Kits during the Randomization Visit and then during the Visits scheduled at the end of the 3rd (Week 11), 6th (Week 23) and 9th (Week 35) treatment cycles, after check of inclusion/exclusion criteria (at Randomization) and discontinuation criteria at the scheduled visits \* (see [Section 6.4.2](#)).

A total number of 13 Patient IMP Kits will be dispensed to each randomized subject as follows:

- at Randomization Visit dispensed 3 Patient Kits for the Cycles 1, 2 and 3
- at Week 11 Visit dispensed 3 Patient Kits for the Cycles 4, 5 and 6
- at Week 23 Visit dispensed 3 Patient Kits for the Cycles 7, 8 and 9
- at Week 35 Visit dispensed 4 Patient Kits for the Cycles 10, 11, 12 and 13

[\* Results of ALT/AST, bilirubin, creatinine, albumin, ECG readings and pregnancy results should be made available by local laboratory in time to allow Patient Kits dispensation as soon as possible during the visit. If this expedite timing cannot be achieved, Patient Kits might be delivered to patient named address by a selected courier (CRO to support shipment). Study drug dispensation will be performed as soon as possible after check of discontinuation criteria.]

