# PPD

## 6. Evaluation of Treatment Compliance and Exposure

### 6.1 Compliance to study treatment regimen

Descriptive analyses of the following parameters will be presented by treatment group for each cycle and during the entire treatment period:

- from IMP dispensation form
  - number of capsules dispensed;
- from IMP accountability form
  - number of returned blisters;
  - number of capsules taken;
  - number of returned unused capsules;
  - IMP intake compliance, ON -treatment period compliance (only by cycle);

Patients are instructed to receive study treatment (either ladarixin or placebo) as follows:

- 400 mg b.i.d (2 capsules at each administration, twice per day);
- for 13 cycles, each lasting 28 days;
- each cycle is composed by 14 consecutive days on-treatment and 14 consecutive days off-treatment.

Calculation of compliance to treatment regimen must consider not only the amount of treatment intake, but also the correct alternation between period “ON” and period “OFF” and their duration. To assess the overall compliance to treatment regimen, the following 3 criteria will be taken into account:

- Compliance to IMP intake;
- Compliance to duration of period “ON” (period of the cycle when the patient is ON treatment);
- Compliance to duration of period “OFF” (period of the cycle when the patient is OFF treatment).

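### OFF-period compliance has an upper limit only and no by-cycle check, so the regimen-compliance flag cannot fail a patient for shortened or skipped breaks

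*SAP*

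**What the plan says.** SAP 6.1 sets the aim, with reference to the ON and OFF parts of each cycle and how long they last: "Calculation of compliance to treatment regimen must consider not only the amount of treatment intake, but also the correct alternation between period". Three global criteria follow, and 6.1.4 classes a subject as compliant with the regimen when all three are met.

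- **Intake (6.1.1.3):** "IMP intake compliance over the entire treatment period in the range 80% - 100% (80 and 100 included"), plus conditions (b) and (c) on the number of out-of-range cycles.
- **ON duration (6.1.2.3):** compliance "over the entire treatment period in the range 80% - 120% (80 and 120 included"), plus the same two by-cycle conditions.
- **OFF duration (6.1.3.3):** the single condition that compliance to OFF-treatment "duration over the entire treatment period is <150" percent.

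On OFF periods, 6.1.3.2 says "No compliance by cycle defined for the" OFF-treatment period. Section 6.1.3.1 gives the denominator, "The total expected duration of period OFF for a subject who complete regularly the study is 168 days", and the numerator: "The total observed duration OFF is given by the sum of the k periods OFF".

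Protocol 6.2 releases kits in batches, beginning with "at Randomization Visit dispensed 3 Patient Kits for the Cycles 1, 2 and 3", then three at Week 11, three at Week 23 and four at Week 35.

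**The concern.** Intake and ON duration are bounded on both sides; OFF duration is bounded only from above. A break that is too long can fail a patient, but one that is too short or absent cannot. Patients hold three or four kits at a time, so nothing in the supply prevents two cycles being taken without the break between them. Neither of the other two criteria responds to this, because each kit is still 56 capsules over 14 days.

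What is at stake is the meaning of one reported result. The Y/N summary by arm would present as adherent to a 14-on/14-off regimen some patients who did not alternate, which is the property that 6.1 says the calculation must capture.

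**Working it through.** **Inputs.** 14 OFF days expected in each of 12 breaks, with OFF duration of cycle k = start of cycle k+1 − last intake of cycle k − 1 (SAP 6.1.3.1). 14 ON days in each of 13 cycles (6.1.2.1). 56 capsules per kit (6.1.1.1). Kits dispensed 3, 3, 3 and 4 (Protocol 6.2). On a 28-day cycle, cycle k is due on day 1 + 28(k − 1), so cycles 4, 7 and 10 are due on days 85, 169 and 253.

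**The plan's own figures.** OFF 14 × 12 = 168 days; ON 14 × 13 = 182 days; capsules 56 × 13 = 728. All three match the SAP. A regular patient scores 100% on each criterion.

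**What the other criteria see.** With kits run together over 13 cycles, intake is 728/728 = 100% (56/56 per cycle) and ON is 182/182 = 100% (14/14 per cycle). Only the OFF total can differ, and it passes at any value from 0 to just under 1.5 × 168 = 252 days.

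**Patterns possible under planned dispensing.** A batch of three kits started on day 1 ends on day 42. If cycle 4 starts on day 85, the OFF period after cycle 3 is 85 − 42 − 1 = 42 days. The waits before cycles 7 and 10 are also 42 days.

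| Pattern | Breaks skipped | OFF days | OFF compliance | Flag now | 80% lower limit on total | 50% lower limit on total |
|---|---|---|---|---|---|---|
| Regular | 0 of 12 | 12 × 14 = 168 | 100% | Y | pass | pass |
| Every batch run together, restarts on days 85, 169, 253 | 9 of 12 | 42 + 42 + 42 = 126 | 126/168 = 75.0% | Y | fail | pass |
| Same, restarts at the visits | 9 of 12 | 28 + 42 + 42 = 112 to 35 + 42 + 42 = 119 | 66.7% to 70.8% | Y | fail | pass |
| Cycles 1–3 together, then treatment stopped | 2 of 2 | 0 of 28 | 0% | Y | fail | fail |
| Cycles 1–3 together, then on schedule | 2 of 12 | 0 + 0 + 42 + 9 × 14 = 168 | 100% | Y | pass | pass |
| First three batches run together, last on schedule | 6 of 12 | 3 × 42 + 3 × 14 = 168 | 100% | Y | pass | pass |

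**Assumptions.**
- The count of 9 is for a patient who finishes each batch before the next is dispensed; kits carried across a visit are not considered.
- Restart at the visits means the first day of the visit week (days 71, 155, 239) or the day after it ends (days 78, 162, 246).
- The 0% takes the discontinuation date as the day of the last cycle-3 dose. If it is d days later, 6.1.3.1 adds d to both parts: d/(28 + d). For d = 29 (day 71) that is 29/57 = 50.9%, still below 80%.

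**Why a limit on the total is not enough.** In the last two rows the wait for the next kits makes up exactly for the skipped breaks. Over the first three breaks, 0 + 0 + 42 = 42 against 3 × 14 = 42 expected, or 100%. Taken break by break, the same patient scores 0%, 0% and 300%. With a two-sided band, such as the 80–120% used for ON, that is three consecutive breaks out of range, which fails a condition modelled on ON (b) (no more than two consecutive). With a lower bound alone it is two, which passes both (b) and (c).

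**The case against.** The strongest case against is that this matters little and is visible elsewhere. Patients record the date and time of each dose and the investigator checks the diary at the next visit (Protocol 6.5, 7.3). Protocol violations are reviewed case by case before unblinding (SAP 5.2). Compliance details are listed by cycle and overall (6.1.5), and exposure duration is summarised (6.2). Efficacy is analysed on the FAS and safety on the SAF; SAP 4.2 defines no per-protocol set, and after early closure all analyses are descriptive. All of this stands, and it limits the point to one summary table. It does not make the flag correct, since none of these sources enters the Y/N rule.

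Three stronger readings are tempting, and the documents do not support them.

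- A reader might infer that a patient could skip every break and dose without interruption through all 13 cycles. The first three kits run out after 3 × 14 = 42 days, before the Week 11 dispensing, so that would need off-schedule supply.
- A reader might infer exposure beyond plan. Total capsules stay at the planned 728; only their timing changes.
- A reader might infer that this is the departure most relevant to safety. No section ranks departures, and Protocol 2.2 says that the toxicity studies support up to 3 months of continuous treatment. One batch gives 42 or 56 consecutive days.

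**Conclusion.** The point holds as a minor inconsistency. The OFF rule does not test what SAP 6.1 says must be tested. Patients who skip 9 of 12 breaks (OFF total 75%, or about 67% to 71% with restarts at the visits), or both breaks before stopping at cycle 3 (0%), are classed as compliant with 100% intake and 100% ON.

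The 0% is a final value only for a patient who stops treatment at that point. For one who continues, the wait for the next kits counts as OFF time and can bring the total back to 100%. How many patients dosed in these ways cannot be known from the documents. The conclusion concerns an analysis classification and says nothing about what length of break is clinically acceptable.

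**What to change.** 1. In 6.1.3.3, make the criterion on the OFF total two-sided. A lower limit of 80%, as in the ON rule, is one option. A limit of 50%, the mirror of 150%, would miss the patient who skips nine breaks.
2. In 6.1.3.2, define OFF compliance by cycle and add conditions modelled on ON (b) and (c), with a two-sided band per break so that a long wait does not hide the skipped breaks before it. The SAP checks (b) and (c) only in patients who completed treatment. Either apply the OFF version to all observed breaks, or accept that early stoppers are judged on the total alone and list them.
3. If the sponsor means to test only for over-long breaks, say so in 6.1.3 and relabel the 6.1.4 output.

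The cost is a line or two in the SAP, using dates already derived for the OFF formula. An 80% limit should not penalise the 15-day ON period that 6.1.2.2 allows for: if the next cycle starts on time, the break is 13/14 = 92.9%. A few patients may move from compliant to non-compliant.
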